## Randomization

Block randomization – A randomization list has been developed that will be used to assign drug (form: ‘Master List-Randomization’). Following enrollment, the subject will be assigned in sequential order. Each block will alternate between each drug (ketamine or fentanyl). Subjects will have 50/50 chance of being assigned to ketamine or fentanyl and will be blinded to which drug they received during the study. After participation in study (meaning they have completed their patient satisfaction score at discharge) subjects will be told what medication they received during the study.

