## 5.0 Resources Available to Conduct the Human Research:

**Describe the resources (facilities, time, emergency resources, etc.) available to recruit, consent, conduct study procedures, and analyze data.**

All recruitment, consent, study procedures and data analysis will be conducted by study investigators at BUMC Phoenix.

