## 6.0 Study Population:

### 6.1 Select all the categories of participants included in the research:

# IRB Protocol for Human Subjects Research

 Healthy adults	 Non-English-speaking subjects
 Non-healthy adults	 UA staff/faculty
 Children (under 18 years old) *	 UA students
 Pregnant women, neonates, and/or fetuses*	 Banner employees
 Prisoners*	 Refugees
 Native Americans, Alaskan Native, and Indigenous Populations*	 Other – please explain: All patients admitted to BUMCP toxicology service diagnosed with RSE
 Adults unable to consent (i.e., cognitively impaired adults) *	

**6.2 For each of the above selected categories, describe the inclusion and exclusion criteria. Indicate age range, gender, and ethnicity.**

Inclusion Criteria

1. Ages  $\geq$  18 years.
2. Able to speak and understand English.
3. RSE requiring IV pain medication for NRS pain score  $> 5$ .
4. No allergy to ketamine or fentanyl.
5. Ability to provide informed consent.
6.  $\leq$  24 hours from envenomation.

Exclusion Criteria

1. Pregnant or lactating.
2. Prisoners.
3. Refugees.
4. History of schizophrenia.
5. Clinically intoxicated.
6. On buprenorphine therapy.
7. History of uncontrolled hypertension.
8. Increased intracranial pressure.
9. Systemic envenomation.

**6.3 Describe the total number of subjects to be enrolled locally. If obtaining specimens, specify the maximum number of specimens needed for this project.**

40 participants.

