# IRB Protocol for Human Subjects

## Research

 Face to face	 Social media
 Flyers	 SONA System
 In person presentations	 TV, Radio, Print
 Online advertisements	 Other – please explain: Click or tap here to enter text.
 Phone calls	

**6.5 Explain the recruitment process. Describe how potential subjects will be identified, where recruitment will take place, when recruitment will occur, and the methods that will be used to recruit individuals.**

Subjects will be identified by the study investigators who are BUMCP physician medical toxicologists and care for RSEs at BUMCP. Subjects will be screened and interviewed using the inclusion/exclusion criteria and if eligible, be asked if they would like to participate in the study. The informed consent form will be reviewed by a trained investigator with the subject/legally authorized representative. To include the voluntary nature of the study, risks/benefits, and study procedures will be explained in detail. Adequate time to review the informed consent form will be given and all questions and concerns will be addressed. The subject/legally authorized representative be given a copy of a signed consent if they choose to participate.

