## Instrument Administration

Patients meeting inclusion criteria will be identified by the study investigators who are BUMCP physician medical toxicologists and care for RSEs. Informed consent, randomization and data abstraction/collection will be obtained by the investigators. Pain scores will be obtained at bedside by investigators at the following intervals; prior to medication administration (zero) and after medication administration at the following intervals 15, 30, 60, and 120 minutes, and a patient satisfaction score at discharge.

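### The only rule stated for the order of the randomization list is alternation, and nothing says who holds the list or how the next assignment is concealed from the investigators who enrol

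*Combined protocol and SAP*

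**What the plan says.** The Randomization paragraph of section 8.2 names the method as block randomization from a list that already exists as a separate form, the Master List. It then gives three rules:

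- On use of the list: "Following enrollment, the subject will be assigned in sequential order".
- On the order of drugs: "Each block will alternate between each drug (ketamine or fentanyl".
- On chance and blinding: "Subjects will have 50/50 chance of being assigned to ketamine or fentanyl and will be blinded to which drug they received during the study".

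On who does the work, section 5.0 says "All recruitment, consent, study procedures and data analysis will be conducted by study investigators at BUMC Phoenix". Section 6.5 says "Subjects will be identified by the study investigators who are BUMCP physician medical toxicologists and care for RSEs at BUMCP". Instrument Administration in section 8.2, and again section 12.5, say "Informed consent, randomization and data abstraction/collection will be obtained by the investigators". The same two places have the investigators take the bedside pain scores.

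The protocol does not state how the list was generated, the block size, whether order is random within or between blocks, who holds the list, how the next assignment is hidden, or whether anyone besides the subject is blinded. The nearest text on custody is in sections 12.7 and 12.8, which limit study documents on hospital computers to the study team. That is the group that enrols.

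**The concern.** Randomization protects the comparison only if the person deciding whether to approach a patient cannot foresee that patient's arm. Here the stated ordering rule is deterministic on its literal reading, and the people who apply it also recruit.

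Eligibility leaves room for judgement. Two exclusions in section 6.2, "Clinically intoxicated" and "Systemic envenomation", are clinical calls. So are the need for IV pain medication and the moment of approach within 24 hours of the bite. A recruiter who expects a particular drug next could, without intending to, be readier to enrol one kind of patient.

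The primary comparison uses the change from time zero to 30 minutes, so steering on baseline pain is partly offset, and other measured factors could be adjusted for. Steering on unmeasured factors could not. The trial is a pilot whose results may be used to plan a larger study, so both a biased estimate and an unsound procedure would carry forward.

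**Working it through.** **Inputs from the protocol.** N = 40 (sections 6.3 and 8.2), 1:1 allocation (20 per arm), two-tailed alpha 0.05, and a clinically significant difference of more than 1.3 points (Statistical Methods). N is set by one-year availability, so there is no sample-size formula to reproduce, and the point does not depend on one. The protocol gives no block size, SD or steering size. Values used for these below are assumptions.

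**What the ordering sentence could mean.**

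1. Drugs alternate patient by patient.
2. Whole blocks are single-drug, and the blocks alternate.
3. Loose wording for balanced blocks in random order.

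Under 1 and 2, equal chance holds at most on average over a random starting drug. Once earlier assignments are known, it does not hold.

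**Step 1: share of assignments guessed correctly when past assignments are visible.**

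- Reading 1: the first is a coin toss and the other 39 are known. (0.5 + 39)/40 = 0.9875.
- Reading 2, length known: the same, 0.9875. If the length must be learned from the first switch, one guess is lost there: (0.5 + 38)/40 = 0.9625.
- Reading 3, known block size, always guessing the arm with more places left in the block. For size 4 the four guesses succeed with probability 1/2, 2/3, 2/3 and 1. The sum is 2.833 per block, so 2.833/4 = 0.708, or 28.3 of 40. Exact enumeration gives 0.750 for size 2 and 0.683 for size 6.
- Blocks of 4 and 6 mixed at random (simulation): about 0.69.
- List readable by the recruiter: 40 of 40 under any reading.

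On reading 3, varying the block size moves the share only from 0.708 to about 0.69. Concealment matters far more.

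**Step 2: illustrative bias.** Suppose a recruiter who expects one drug enrols patients whose expected change is higher by g NRS points, and lower by g when expecting the other. With share p guessed correctly, the mean shift is g(2p − 1) in one arm and −g(2p − 1) in the other, so bias = 2g(2p − 1).

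- Alternation (p = 0.9875, 2p − 1 = 0.975): 0.49 points at g = 0.25 and 0.98 at g = 0.5. These are about 38% and 75% of the 1.3-point threshold.
- Balanced blocks of 4 (p = 0.708, 2p − 1 = 0.417): 0.21 and 0.42 points.

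**Step 3: illustrative type I error.** Two-sample t-test, 20 per arm, 38 df, two-sided 0.05, noncentrality = bias / (SD × √(2/20)). The t-test stands in for the rank test that the protocol names.

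| Sequence | g | SD 2.0 | SD 2.5 | SD 3.0 |
|---|---|---|---|---|
| Alternation | 0.25 | 11.7% | 9.2% | 7.9% |
| Alternation | 0.5 | 32.4% | 22.5% | 17.1% |
| Blocks of 4 | 0.25 | 6.2% | 5.8% | 5.5% |
| Blocks of 4 | 0.5 | 9.8% | 8.1% | 7.1% |

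The table assumes that every enrolment is steered. Under alternation with g = 0.5 and SD 2.5, steering half of enrolments gives 9.2%, a quarter 6.0% and a tenth 5.2%.

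**The case against.** The strongest reply is that the deciding document has not been seen. The Master List may already hold randomly permuted blocks, and the block label, the equal-chance statement and the ticked randomization box all show an intent to randomize. Patient-by-patient alternation would need neither blocks nor a list. This stands as a reason not to assert that the list is non-random. It does not remove the problem: the one ordering rule given to staff still says alternate, and a random list read by the enrolling team is not concealed.

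The protocol also assigns after enrolment, which is the right order of events and already covers part of the remedy. It does not hide a predictable next assignment from the person choosing whom to approach.

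Two points limit the likely size. Forty patients in a year is about one every nine days (365/40 = 9.1), so there will seldom be a second patient to swap, and steering would mostly mean passing over a scarce eligible patient. The type I figures rest on an assumed steer and SD, and they fall close to 5% when few enrolments are affected.

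Finally, this is a feasibility pilot. That lowers the inferential stakes, but the plan still sets a between-group test at 0.05 and a clinical threshold, and its results may shape the next trial.

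**Conclusion.** The concern holds. Followed literally, the stated rule gives a predictable sequence (96% to 99% of assignments guessable if past ones are visible), and no concealment is stated on any reading. On the benign reading, about 68% to 75% remain guessable with known blocks of 2 to 6, and all 40 if the list is open to the enrolling team.

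That conclusion needs no assumption about steering or SD. The bias figures (0.49 or 0.98 points under alternation) and the type I error range (8% to 32% with every enrolment steered, lower with partial steering) are illustrations only. Whether the actual list alternates cannot be settled from the documents.

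This must be fixed before enrolment, because allocation cannot be repaired afterwards. If the list does alternate, the trial is quasi-randomized despite its label.

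**What to change.** In section 8.2:

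- Delete the sentence saying that blocks alternate.
- Check the Master List. Unless it is already in random order within blocks, replace it with computer-generated, randomly permuted blocks of undisclosed, randomly varying size, for example 4 and 6.
- Have the list prepared and held by someone who does not enrol patients, and name that role.
- Release each assignment from sequentially numbered, sealed, opaque envelopes, opened only after consent is signed and the baseline NRS is recorded.
- State who is blinded besides the subject.

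If the existing list is already random within blocks, only the wording, custody and concealment need to change.

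The cost is a short task for one non-enrolling colleague, 40 envelopes and a few sentences. With mixed blocks of 4 and 6, stopping at 40 inside a block can leave the arms at most 2 patients apart (21 v 19; mean difference about 0.5 in simulation). Stopping earlier could leave a difference of up to 3.

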## Statistical Methods

Differences between pain scores at time zero (before drug administration) and at time 30 minutes will be compared between the fentanyl and ketamine group using a Wilcoxon Signed Ranks Test, using a two-tailed alpha of 0.05.

Significant clinical difference will be defined as an absolute difference between groups of greater than 1.3 (using confidence interval of 95%). This difference is commonly accepted as the minimum clinical difference in subjective pain scales [5].

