## 3.0 Purpose:

**Describe the purpose, specific aims, objectives, questions to be answered, hypotheses, and/or primary and secondary study endpoints of the Human Research.**

The purpose of this study is to evaluate differences in pain levels following a single administration of fentanyl or ketamine to treat pain after rattlesnake envenomation. The aim is to assess pain scores prior to medication administration, then 15, 30, 60, and 120 minutes after single medication administration. Primary endpoint is pain score at 30 minutes after medication administration. Secondary endpoints are pain scores at additional time points, need for rescue medication, adverse medication effects, and patient pain satisfaction scores at discharge.

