**Primary hypothesis**

There will be no difference in pain responses in the two groups.

Fentanyl and ketamine are commercially available and used as FDA approved for the management of pain in the United States.

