# IRB Protocol for Human Subjects Research

## 13.0 Additional Questions (complete as applicable):

**13.1 Subject Injury:** If the research involves more than minimal risk to subjects, describe the provisions for medical care and available compensation in the event of research related injury. If the Human Research has a clinical trial agreement, this language should reflect what is stated in the agreement.

The investigators have no funds set aside for the payment of treatment expenses for this study. The study is examining pain outcomes from the commercially available drugs. If injury is experienced by subjects, they may be treated by the investigator as part of standard care.

**13.2 Withdrawal of Subjects:** Discuss how, when, and why subjects may be removed from the study. If abrupt withdrawal is necessary, discuss how subjects will be withdrawn so that they are not put at increased risk. Discuss what happens if a subject is withdrawn from one part of the study but asked to continue with other parts, such as ongoing follow-up.

Subjects may be withdrawn from study by investigators at any time if patient is at increased risk. Subjects can also withdraw consent at any time. Subjects will then continue to be monitored as part of standard care and data collected for the study may be used for the analysis.

**13.3 Monitoring for Subject Safety:** Provide a brief lay discussion of your plan to monitor for subject safety. Describe what safety information will be collected, including serious adverse events, how safety information will be collected, and the frequency of collection including a timeline of when the data and review(s) will occur, who will review the information, and the plan for reporting findings.

If there will not be a way to monitor for subject safety, please explain.

Subjects will be monitored for safety at the study visit by investigators. Follow up monitoring will be done as part of routine care.

Adverse events will be monitored to ensure the safety of each subject while on the study. The site investigator will report any unanticipated adverse events to IRB according to their reporting requirements.

**13.4 Data Management Plan:** Please discuss the data management plan if required by your funding agency. For additional resources, reference the HSPP [Data Management webpage](#).

NA

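### The primary comparison of two independent randomised arms is assigned a Wilcoxon signed-rank test, and the plan gives no pairing rule

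*Combined protocol and SAP*

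**What the plan says.** Section 8.2, Statistical Methods, takes "Differences between pain scores at time zero (before drug administration) and at time 30 minutes" as the quantity to analyse. It says these "will be compared between the fentanyl and ketamine group using a Wilcoxon Signed Ranks Test", with a two-sided alpha of 0.05. The same section calls a between-group difference above 1.3 points clinically significant and refers to a 95% confidence interval. It does not say how the difference or the interval is to be calculated.

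The design is parallel-group. Section 3.0 sets out to "evaluate differences in pain levels following a single administration of fentanyl or ketamine", and the primary hypothesis is that "There will be no difference in pain responses in the two groups". Under Randomization in section 8.2, "Subjects will have 50/50 chance of being assigned to ketamine or fentanyl" and "Following enrollment, the subject will be assigned in sequential order". The list is described as blocked, with each block alternating between the drugs, but no block size is given and blocks are not mentioned in the analysis. The total is 40 patients, set by availability over one year.

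**The concern.** The signed-rank test works on one set of differences: either a patient's own before-and-after scores, or the differences within matched pairs. Across the two arms this trial has neither. Nobody receives both drugs, and no ketamine patient is matched to a fentanyl patient. The test for two independent samples of changes is the Wilcoxon rank-sum (Mann-Whitney) test, so the wording may be a naming slip.

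It still matters, because this is the only hypothesis test in the plan and it belongs to the primary endpoint. Someone who follows the text has to choose between a within-arm test that leaves the between-arm hypothesis untested and a pairing of their own making. In the second case the p-value can depend on a choice made after the data are seen.

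There is a related gap. The 1.3-point rule needs an estimated difference with a confidence interval, and a p-value from either test supplies neither.

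**Working it through.** There is no planned figure to reproduce: the 40 patients come from availability, not from a power calculation. The check is first of the design text and then of how each literal reading behaves.

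**1. Can the arms be paired?** One drug per patient (sections 3.0 and 8.2) rules out crossover. No section describes matching. Blocks could act as pairs only if the block size were two and the analysis were by block; the plan states neither. The arms are therefore independent.

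**2. Inputs.** From the documents: 40 patients at 1:1, so 20 per arm; integer NRS 0-10; entry score above 5, so baseline 6-10; two-sided alpha 0.05; 1.3-point threshold. Assumed, because the documents give no values: SD of change 2.0 / 2.5 / 3.0, a mean fall of 2 in the reference arm, and scores capped at 0-10. There were 4,000 simulated trials per setting, using normal approximations with tie correction and zeros dropped for the signed-rank test. Capping shrinks a nominal 1.3-point difference to 1.1-1.2 and a nominal 2-point difference to 1.7-1.9.

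**3. Reading (a): within-arm tests of time zero against 30 minutes.** Share of trials with both arms significant:

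| True falls | SD 2.0 | SD 2.5 | SD 3.0 |
|---|---|---|---|
| 2 v 2 (identical drugs) | 99% | 94% | 86% |
| 4 v 2 (nominal) | 100% | 97% | 92% |

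Doubling the fall in one arm moves the result by only 1 to 6 points, so it says almost nothing about ketamine against fentanyl. If all 40 changes are pooled into one signed-rank test, it rejects in 100% of trials with identical drugs (assumed fall 2.5, SD 1.5 to 3.0).

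**4. Reading (b): cross-arm pairs.** With d_i = (change of ketamine patient i) − (change of the fentanyl patient paired with i), the test ranks |d_i| and sums the signed ranks. If the pairing ignores outcomes:

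| | Signed-rank | Rank-sum |
|---|---|---|
| Type I error (SD 2.0 to 3.0) | 4.8-5.2% | 4.9-5.2% |
| Power, nominal 1.3 points, SD 2.5 | 33% | 34% |
| Power, nominal 2 points, SD 2.5 | 63% | 65% |

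Average error rates are not the problem.

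**5. Dependence on the pairing.** Twenty patients per arm can be paired in 20! ≈ 2.4 × 10^18 ways. If f is the share of pairings of one data set that give p < 0.05, two random pairings disagree with probability 2f(1−f). Averaged over 300 data sets with 100 pairings each at SD 2.5, this is 4% with identical arms, 9% at 1.3 points and 12% at 2 points. Repeat runs gave about 4%, 10% and 9-11%.

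Two data sets chosen to be borderline, with 5,000 random pairings each, show the spread:

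- SD 2.0, rank-sum p = 0.059: signed-rank p ran from 0.003 to 0.21, with 30% of pairings below 0.05.
- SD 2.5, rank-sum p = 0.055: signed-rank p ran from 0.004 to 0.26, with 16% below 0.05.

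**6. Missing scores.** Section 13.2 says that "Subjects can also withdraw consent at any time". If a fraction q of patients lack a 30-minute score, pairing by list order loses on average 20 × [1 − (1 − q)²] pairs. The chance of unequal arms is 1 minus the sum of squared binomial(20, q) probabilities.

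| q (assumed) | Pairs lost of 20 | Arms unequal |
|---|---|---|
| 2.5% | 20 × (1 − 0.9506) = 1.0 | 54% |
| 5% | 20 × (1 − 0.9025) = 2.0 | 69% |
| 10% | 20 × (1 − 0.81) = 3.8 | 79% |

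Each broken pair also discards a patient whose score was observed. The rank-sum test uses every observed change and does not need equal arms.

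**The case against.** The strongest reply is that this is a slip for rank-sum and any competent analyst would read it so. The sentence speaks of comparing the two groups, the hypothesis is a two-group one, and only the test's name conflicts. That is plausible, but running the rank-sum test would still depart from the written plan.

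Second, the measured harm is limited. Outcome-blind pairing holds type I error near 5% and loses 1 to 2 points of power. A pairing rule fixed in advance, such as list order, would leave no latitude. This stands: the 4% to 12% disagreement measures the latitude left when no rule is set, and the plan sets none. The within-arm figures likewise show what that reading would test, not what the trial is likely to report.

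Third, the SD, mean fall and missing rates are assumptions. Scores are collected at the bedside, and data collected before withdrawal may be used. So withdrawal need not cost a 30-minute score, although a score never taken cannot be recovered. The figures are illustrative; the mismatch between test and design does not rest on them.

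Fourth, this is a feasibility pilot. Even so, it sets a two-sided 0.05 test and a 1.3-point decision rule, and its results may be used to plan a larger study.

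Finally, Hodges-Lehmann is not the only acceptable estimator; a baseline-adjusted model would also serve. It is recommended because it goes naturally with the rank-sum test.

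**Conclusion.** The concern holds and should be fixed before analysis. The only named hypothesis test, on the primary endpoint, is of the wrong type for two independent arms, and nothing in the plan supplies the pairing it would need. This follows from the design text alone.

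The size of the consequence rests on the assumed SDs, mean fall and missing rates. The within-arm reading does not test the stated hypothesis. The cross-arm reading is close to rank-sum on average, but its p-value depends on an unstated choice, and it loses patients whenever a pair is broken. No claim is made of inflated type I error or of a material loss of power under outcome-blind pairing. The missing estimator for the 1.3-point rule is a secondary gap that the same edit can close.

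**What to change.** In section 8.2, Statistical Methods, replace the signed-rank test with the Wilcoxon rank-sum (Mann-Whitney) test on the change from time zero to 30 minutes, two-sided alpha 0.05. Add that the Hodges-Lehmann between-arm difference, with its 95% confidence interval, is the estimate to which the 1.3-point rule is applied.

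The cost is one or two sentences. Data collection, alpha and the 40 patients are unchanged. With 20 per arm and a nominal 1.3-point difference, the corrected test has simulated power of about 71%, 49%, 33% and 25% at assumed SDs of 1.5, 2.0, 2.5 and 3.0 (assumed fall 2.5). The correction settles which test is run but does not add power.

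This wording keeps the variable that Statistical Methods already names. Section 3.0 gives the primary endpoint as the score at 30 minutes rather than the change; that is a separate point, best reconciled in the same edit.
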